8.2 Secondary Efficacy Analyses

Secondary efficacy endpoints are the percent change from baseline to Week 12 in each assessment parameter (HDL-C, non-HDL-C, TC, TG, apo B, hsCRP, and HbA1c), the proportion of subjects whose LDL-C value achieves the lipid management goal based on risk assessment at Week 12, and the proportion of subjects whose LDL-C value achieves <70 mg/dL at Week 12.

For the percent change from baseline to Week 12 in each assessment parameter (HDL-C, non-HDL-C, TC, TG, apo B, hsCRP, and HbA1c), analysis of covariance will be performed using treatment group and the randomization stratification factor (statin tolerance/statin intolerance) as factors and the baseline value for each assessment parameter as a covariate. The least squares mean for each treatment group and the differences in the mean of the least squares between each ETC-1002 group and the placebo group, together with the two-sided 95% confidence intervals, will be calculated. The same analysis will also be performed for the percent change in each assessment parameter from baseline at each visit (Week 2, Week 4, Week 6, Week 8, and Week 12) using measured OC data. In addition to for the primary endpoint LDL-C, the timecourse of the least squares mean \pm standard error for the percent change from baseline in each assessment parameter (HDL-C, non-HDL-C, TC, TG, apoB, hsCRP, HbA1c, and LDL-C [calculated by Friedewald formula]) at each visit from baseline to Week 12 in the treatment period will be plotted for each treatment group. The same timecourses will also be plotted by the randomization stratification factor (statin response).

The proportion of subjects whose LDL-C value achieves the lipid management goal (<100 mg/dL [history of coronary artery disease or heterozygous familial hypercholesterolemia], <120 mg/dL [high risk], or <140 mg/dL [intermediate risk]) at Week 12, and the proportion of subjects whose LDL-C value achieves <70 mg/dL at Week 12 will be analyzed by Cochran-Mantel-Haenszel test stratified by statin response (statin tolerance/statin intolerance) to calculate the differences between each ETC-1002 group and the placebo group and the two-sided 95% confidence intervals (based on

Cochran-Mantel-Haenszel). The proportion in each treatment group and the two-sided 95% interval (based on Clopper-Pearson method) will also be calculated. The same analysis will also be performed for the proportion of subjects whose LDL-C value achieves the lipid management goal and the proportion of subjects whose LDL-C value achieves <70 mg/dL at each visit (Week 2, Week 4, Week 6, Week 8, and Week 12) using measured OC data. For the proportion of subjects whose LDL-C value achieves the lipid management goal at Week 12 and the proportion of subjects whose LDL-C value achieves <70 mg/dL at Week 12, the proportion in each treatment group and the two-sided 95% interval (based on Clopper-Pearson method), together with the differences of proportion between each ETC-1002 group and the placebo group and the two-sided 95% confidence intervals (based on score statistic) will be calculated by the randomization stratification factor (statin response). The same analysis will also be performed at each visit (Week 2, Week 4, Week 6, Week 8, and Week 12) using measured OC data.

For other efficacy endpoints including the measured value and change and percent change from baseline at each visit for each assessment parameter (LDL-C, HDL-C, non-HDL-C, TC, TG, apo B, hsCRP, and HbA1c), descriptive statistics (number of subjects, mean, standard deviation, median, minimum, and maximum) by treatment group will be calculated at each visit (Week 2, Week 4, Week 6, Week 8, Week 12, and Week 16 [FU]). The same descriptive statistics will also be calculated for LDL-C calculated by the Friedewald formula ($TC - HDL-C - TG/5$). The timecourse of the mean \pm standard deviation for the percent change from baseline in each assessment parameter (LDL-C, HDL-C, non-HDL-C, TC, TG, apo B, hsCRP, HbA1c, and LDL-C [calculated by Friedewald formula]) at each visit from baseline to Week 12 in the treatment period will be plotted for each treatment group. The same timecourses will also be plotted by the randomization stratification factor (statin response).

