5.2.1 Inclusion Criteria

Subjects are required to meet the following inclusion criteria when assessed:

- 1) Patients from whom written informed consent is obtained prior to start of the trial
- 2) Patients, either male or female, age 20 years or older and younger than 75 years at the time of informed consent
- 3) Patients who meet the following criteria for statin tolerance or statin intolerance
 - Statin tolerance
Patients with hypercholesterolemia who have been taking statins (atorvastatin, pitavastatin, rosuvastatin, pravastatin, simvastatin, or fluvastatin) and hypercholesterolemia drugs other than statins if necessary, at the same dose and regimen from at least 4 weeks prior to Week -5 (Visit S1) (at least 6 weeks, for fibrates and selective PPAR α modulators) to Week -5 (Visit S1) according to the approved regimen, but fail to achieve the lipid management goals of LDL-C based on risk assessment shown in the inclusion criteria 4) at both Week -5 (Visit S1) and Week -1 (Visit S3)
 - Statin intolerance
Patients with hypercholesterolemia in whom safety problems occurred when administration of statins was started or increased in dose and were resolved after discontinuation or dose reduction of statin administration, and who have been taking statins at (or below) the lowest approved daily dose and/or who have been taking at least one hypercholesterolemia drug other than statins at the same dose and regimen from at least 4 weeks prior to Week -5 (Visit S1) (at least 6 weeks, for fibrates and selective PPAR α modulators) to Week -5 (Visit S1) according to the approved dosage regimen, but fail to achieve the lipid management goals of LDL-C based on risk assessment shown in the inclusion criteria 4) at both Week -5 (Visit S1) and Week -1 (Visit S3)
- 4) Patients considered to be at risk of developing cardiovascular events who meet any of the following conditions a), b), or c)
 - a) Patients with either of the following medical histories or complications and in whom LDL-C at Week -5 (Visit S1) and Week-1 (Visit S3) is ≥ 100 mg/dL
 - History of coronary artery disease
 - Diagnosed with heterozygous familial hypercholesterolemia (HeFH)

- b) Patients with any of the following medical histories or complications and in whom LDL-C at Week -5 (Visit S1) and Week-1 (Visit S3) is ≥ 120 mg/dL
 - Diagnosed with peripheral arterial disease
 - History of non-cardiogenic cerebral infarction

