9.4.1.3 Secondary Efficacy Endpoint Analysis

Secondary efficacy endpoints are the percent change from baseline to Week 12 in each assessment (HDL-C, non-HDL-C, TC, TG, apo B, hsCRP, and HbA1c), the proportion of subjects whose LDL-C value achieve the lipid management goals based on risk assessment at Week 12, and the proportion of subjects whose LDL-C value achieve <70 mg/dL at Week 12.

For the percent change from baseline to Week 12 in each assessment (HDL-C, non-HDL-C, TC, TG, apo B, hsCRP, and HbA1c), analysis of covariance will be performed using treatment group and the randomization stratification factor (statin tolerance/statin intolerance) as factors and the baseline value of each assessment as a covariate. The least squares mean of each treatment group and differences in mean of least squares between each ETC-1002 group and the placebo group as well as their two-sided 95% confidence intervals will be calculated. The proportion of subjects whose LDL-C value achieve the lipid management goals based on risk assessment at Week 12, and the proportion of subjects whose LDL-C value achieve <70 mg/dL at Week 12 will be analyzed by the Cochran-Mantel-Haenszel test stratified by statin response (statin tolerance/statin intolerance). The proportion in each treatment group and its two-sided 95% interval, as well as the differences of proportion between each ETC-1002 group and the placebo group and their two-sided 95% confidence intervals will be calculated.

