3.4 Trial Visit Window

Data observed at CRF Visit will be used at each analysis visit (but data at discontinuation will not be used in analysis). Data from unscheduled visits will not be used. Efficacy analysis will be performed using the data obtained up until 2 days after final IMP administration. In assessment of efficacy endpoints, baseline for fasting lipid parameters is defined as the mean of the values for Day 1 (Visit T1) and Week -1 (Visit S3). If only one value is obtained, that value will be used as baseline. For efficacy endpoints other than fasting lipid parameters, baseline is defined as the value for Day 1 (Visit T1). For safety endpoints, baseline is defined as the last data obtained prior to initial IMP administration in the treatment period.

4 Sample Size

Differences in the percent change in LDL-C from baseline to Week 12 in the ETC-1002 group versus the placebo group in non-Japanese phase 3 trials were -18.1% and -17.42% in trials in statin tolerant subjects and -21.41% and -28.45% in trials in statin intolerant subjects. Based on the results, the difference between the ETC-1002 group and the placebo group in the subjects with statin tolerance was assumed to be 17% , and the difference between the ETC-1002 group and the placebo group in the subjects with statin intolerance was assumed to be 25% . For the present trial it was assumed that the percentage of statin intolerant subjects enrolled would be 20% and that the difference in the endpoint between the ETC-1002 group and the placebo group would be 19% in the overall trial population. Based on the results of the phase 3 trials, assuming a difference of 19% with standard deviation of 25% between the ETC-1002 groups and the placebo group in the percent change in LDL-C from baseline to Week 12, 38 subjects per group are required to achieve a power of 90% or higher in a two-tailed test with a 5% significance level. Assuming a withdrawal rate of 12.5% , the target number of subjects to be randomized was set at 44 per group.

5 Statistical Analysis Datasets

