8.1.1 Primary Efficacy Analysis

For the primary analysis of the primary endpoint, analysis of covariance will be performed using treatment group and statin response (statin tolerance/statin intolerance), the randomization stratification factor, as factors and baseline value of LDL-C as a covariate. The overall Type I error rate will be controlled by performing comparison versus the placebo group starting from the highest ETC-1002 dose group by a closed testing procedure at a two-sided significance level of 0.05. Baseline is defined as the mean of the LDL-C values for Day 1 (Visit T1) and Week -1 (Visit S3). If only one value is observed, that value will be used as baseline. In the analysis of covariance described above, the least squares mean for each treatment group and the differences in the mean of the least squares between each ETC-1002 group and the placebo group, together with the two-sided 95% confidence intervals, will be calculated. The same analysis will also be performed for the percent change in LDL-C from baseline at each visit (Week 2, Week 4, Week 6, Week 8, and Week 12) using measured values (Observed case, OC).

The percent change in LDL-C from baseline to Week 12 will be tested using a contrast for low-dose saturation (L-end), medium-dose saturation (M-end), and linear (L-end: 3-1-1-1, M-end: 5 1-3-3, Linear: 3 1-1-3) to investigate the dose-response relationship between placebo and ETC-1002 low dose, medium dose, and high dose. Multiplicity will not be considered in the analyses for dose-response relationship.

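### The Week 12 LDL-C goal-attainment comparison is valid, but less precise than the collected data allow because it ignores how far above goal each subject started

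*SAP*

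**What the plan says.** SAP 8.2 states that the two LDL-C threshold proportions at Week 12 (attainment of the subject's own goal, and LDL-C <70 mg/dL) "will be analyzed by Cochran-Mantel-Haenszel test stratified by statin response (statin tolerance/statin intolerance". It takes the difference from placebo and its 95% CI from the same method. Protocol 9.4.1.3 names the same test: "will be analyzed by the Cochran-Mantel-Haenszel test stratified by statin response (statin tolerance/statin intolerance". SAP 8.2 repeats the goal analysis by visit on observed cases and separately within each statin-response stratum, again without baseline LDL-C.

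The goal is 100, 120 or 140 mg/dL according to risk category. Under Protocol 5.2.1, subjects qualify because they "fail to achieve the lipid management goals of LDL-C based on risk assessment" at both Week -5 and Week -1.

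The continuous endpoints are handled differently. The primary ANCOVA (SAP 8.1.1) and the MMRM (SAP 8.1.2) include baseline LDL-C, and the ANCOVAs for the other parameters use "the baseline value for each assessment parameter as a covariate". The value needed for the goal endpoint already exists: "Baseline is defined as the mean of the LDL-C values for Day 1" and Week -1.

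Randomisation is stratified by statin response only (Protocol 6.3).

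**The concern.** A subject who starts 3% above goal and one who starts 50% above goal have very different chances of finishing below it, whatever the treatment. Distance to goal is therefore a prognostic variable by construction. Neither the randomisation nor the analysis takes it into account, although it is measured in everyone. Leaving it out moves explainable outcome variation into the standard error of the risk difference.

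At stake is the width of the interval for a secondary endpoint that expresses the LDL-C result against each patient's own target, in a trial meant to inform the phase 3 dose.

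**Working it through.** **Inputs from the documents.** SAP Section 4: "assuming a difference of 19% with standard deviation of 25% between the ETC-1002 groups and the placebo group"; 17 in statin-tolerant and 25 in statin-intolerant subjects; 20% intolerant; 12.5% withdrawal; 44 randomised per group. SAP 8.2: goals of 100, 120 and 140 mg/dL.

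**The plan's own figure.** The plan states that "38 subjects per group are required to achieve a power of 90% or higher in a two-tailed test with a 5% significance level".
- Weighted effect: 0.8 × 17 + 0.2 × 25 = 18.6, rounded to 19.
- Normal approximation: 2 × (25/19)² × (1.960 + 1.282)² = 36.4, so 37.
- Exact two-sample t-test: power is 89.7% at 37 and 90.5% at 38, so 38 reproduces.
- Withdrawal: 38 / (1 − 0.125) = 43.4, so 44.

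This sizing concerns the percent change in LDL-C. The documents give no power figure for goal attainment.

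**Assumptions not in the documents.** Baseline/goal = 1 + a gamma-distributed excess (shape 1.5) with mean 15%, 25% or 40%. Goal categories are in the ratio 50/35/15%. Percent change is independent of baseline and averages zero on placebo.

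**Simulation.** One dose versus placebo, 38 per arm, 8 of 38 statin-intolerant, 2,000 trials per setting. Week 12 LDL-C = baseline × (1 + percent change/100); success means below own goal. Two analyses were compared:
- the planned stratified Mantel-Haenszel risk difference and CMH test;
- a logistic model with treatment, statin response and log(baseline/goal), standardised to a marginal risk difference with an influence-function SE.

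Results at effect 19 and SD 25:

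| Mean excess over goal | Placebo / active attainment | Risk difference, planned / adjusted | Empirical SD, planned / adjusted | Variance ratio | Power, planned / adjusted |
|---|---|---|---|---|---|
| 15% | 32.2% / 60.4% | 0.282 / 0.283 | 0.1080 / 0.1052 | 0.949 | 71.0% / 74.4% |
| 25% | 25.6% / 51.5% | 0.259 / 0.259 | 0.1088 / 0.1040 | 0.914 | 64.0% / 70.7% |
| 40% | 19.2% / 41.7% | 0.226 / 0.225 | 0.0999 / 0.0938 | 0.883 | 57.7% / 65.5% |

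Monte Carlo error on a power figure is about √(0.64 × 0.36 / 2000) = 1.1 points.

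**In subjects, at 44 per arm.** 44 × (1/ratio − 1) gives 44 × (1/0.949 − 1) = 2.4, 44 × (1/0.914 − 1) = 4.1 and 44 × (1/0.883 − 1) = 5.8. Rounded up, that is 3 to 6.

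**In interval width, middle row, 38 per arm.** 1.96 × 0.1088 = 21.3 points against 1.96 × 0.1040 = 20.4 points.

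**Type I error (4,000 null trials, excess 25%).** At SD 25: CMH 4.7%, adjusted Wald test 5.3%. At an assumed SD of 15: 5.7% and 6.4%.

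**Second set of assumptions.** 44 per arm, mean baseline/goal ratio 1.21 to 1.38 with SD 0.14 to 0.27, within-subject CV 8%, selection at both screening visits. At SD 25 the variance ratios were 0.94, 0.92 and 0.90, and power rose 3 to 4 points.

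**The <70 mg/dL endpoint.** At SD 25, attainment was 2.5% to 4.5% on placebo and 10.8% to 16.8% on active, and the variance ratios were 0.995 to 1.007: no gain. In the sparsest setting (SD 15, excess 40%) the adjusted SE was too small, averaging 0.0235 against an empirical SD of 0.0332.

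**The case against.** The strongest reply is that nothing here is wrong. CMH stratifies by exactly the factor used in randomisation, is unbiased over randomisation and held its level near 5%. The endpoint is one of several secondary objectives, Protocol 9.4.1.2 names no key secondary endpoint, and the closed testing procedure covers only the primary endpoint. No power was promised for goal attainment, so none is missed. The baseline-adjusted LDL-C effect is already the primary analysis. All of this stands and limits the weight of the point.

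The gain is also modest: in the middle case the half-width shrinks by about 1 point out of 21. That stands too. It does not remove the case for a change that needs no new data.

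Three stronger readings are tempting and are not supported:
- **Chance imbalance as a separate harm.** A one-SD imbalance in distance to goal moves the planned estimate by 2.6 to 3.3 points at SD 25. This variation is already inside the planned interval. In the middle case (3.3/10.88)² = 9%, which is essentially the 8.6% variance reduction seen from the other side. Counting both counts one loss twice.
- **A loss of up to about 11 subjects per arm.** That needs a variance ratio near 0.80, since 44 × (1/0.80 − 1) = 11. Such a ratio arose only with an SD of 15, and the plan uses 25.
- **CMH should be replaced.** The adjusted Wald test ran slightly above CMH in the null simulations reported above, so it is not the better primary test in samples of this size. Nor does risk category play no part at present: it sets each subject's goal and so defines the outcome.

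**Conclusion.** The point holds as one of efficiency. The planned comparison is valid and estimates the same marginal risk difference as the adjusted one, but with more variance than necessary. At the plan's effect of 19 and SD of 25, adjustment lowers that variance by about 5% to 12%, worth roughly 3 to 6 subjects per arm of 44, and raises power by about 3 to 8 points. A small part of the power difference may reflect the adjusted test's slightly higher type I error, so the variance figure is the firmer measure.

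The size rests on an assumed baseline-to-goal distribution (mean excess 15% to 40%) and on percent change being independent of baseline; the documents give neither. A reader might infer from the contrast with the baseline-adjusted continuous endpoints that the binary analysis is mistaken. The documents do not support that: an unadjusted stratified comparison of randomised groups is sound. The finding does not extend to the <70 mg/dL endpoint. It is an optional-to-recommended improvement.

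**What to change.** Keep the CMH test stratified by statin response. In SAP 8.2, prespecify one additional estimate for Week 12 goal attainment: the standardised (marginal) difference in proportions between each ETC-1002 group and placebo. Take it from a logistic model with treatment group, statin response and log(baseline LDL-C / own goal), using the efficacy baseline of SAP 3.4 and the imputation rule of SAP 5.4. Name the interval method: a robust (influence-function) or bootstrap 95% CI. Record the addition in SAP Section 14, before unblinding. Leave the <70 mg/dL endpoint and the by-visit and by-stratum analyses as planned.

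Cost: a few lines of SAP text and code, and no new data. Downside: one more estimate to report, and an adjusted Wald test that may run slightly above 5% in small samples, which is why CMH stays as the test. The precision gain then shows in the adjusted estimate and its interval; the CMH p-value is unchanged.

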6.3 Measures to Minimize/Avoid Bias

In this trial [REDACTED]

the treatment period will be conducted in a double-blind manner. [REDACTED]
[REDACTED]
[REDACTED]

In the treatment period, stratified randomization by statin response (statin tolerance /statin intolerance) will be performed to minimize influence on evaluation. Subjects will be randomized to each group in a ratio of 1:1:1:1. Details of randomization will be provided in a separate procedure. Neither the subject nor the investigator/subinvestigator will be informed of the IMP randomization code. The persons involved in the trial of the sponsor, including the contract research organization (CRO) (except the bioanalytical laboratory), cannot know the IMP randomization code during the trial period.

Indistinguishability of the IMP will be confirmed by the IMP packaging company and the sponsor before the start of the trial.

The randomization table will be stored securely until unblinding after all eCRFs and database lock.

The emergency code will be managed by the Interactive Web Response System (IWRS) until the end of the trial. If a medical emergency occurs to a subject and it is determined that knowledge of the IMP randomization code is important for the treatment of the subject, emergency code will be obtained according to [Section 8.8.7](#).

Plasma drug concentrations will not be disclosed until unblinding at the end of the trial. These measurements will be performed at a specific bioanalytical laboratory and will not be performed at the clinical laboratory of the trial site.

Maintenance of blinding for efficacy endpoints will be found in [Section 8.1](#).

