3.3 Trial Population

This trial will be conducted in Japanese patients with hypercholesterolemia who are aged 20 years or older and younger than 75 years at the time of informed consent and who are being treated with hypercholesterolemia drugs but have inadequate control and cannot achieve the lipid management goal. Subjects [REDACTED]
[REDACTED]
[REDACTED]

[REDACTED] those confirmed by the investigator or subinvestigator not to fall under the exclusion criteria will be randomized. The target number of randomized subjects is 176 in total (44 in the ETC-1002 60-mg/day group, 44 in the 120-mg/day group, 44 in the 180-mg/day group, and 44 in the placebo group). In addition to patients with statin tolerance, patients with statin intolerance will be enrolled at $\geq 20\%$ of the total. Statin response (statin tolerance/intolerance) is set as a randomization stratification factor so that subjects with statin intolerance will be equally allocated to each treatment group.

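### For LDL-C <70 mg/dL, the overall Mantel-Haenszel interval falls 1 to 2.5 points short of 95% coverage if placebo events are few and the drug works; a stratified score interval would restore it

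*SAP*

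**What the plan says.** SAP 8.2 treats two LDL-C responder endpoints alike: reaching the risk-based lipid goal, and reaching <70 mg/dL, both at Week 12. Each "will be analyzed by Cochran-Mantel-Haenszel test stratified by statin response". The difference between each ETC-1002 group and placebo gets a two-sided 95% interval that is also described as Cochran-Mantel-Haenszel based. No variance formula, continuity correction or rule for zero events is given.

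Two other intervals in the same section use methods suited to small counts. Each arm's proportion gets a Clopper-Pearson interval. For the difference within each statin-response stratum, the "confidence intervals (based on score statistic) will be calculated by the randomization stratification factor". Only the overall stratified difference stays on the large-sample method.

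Missing Week 12 values are carried forward for these endpoints (SAP 5.4), so close to 44 subjects per arm are analysed.

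**The concern.** Reaching <70 mg/dL is a demanding target here. Protocol 5.2.1 requires screening LDL-C of at least 100, 120 or 140 mg/dL depending on risk group. From those floors, falling below 70 means a drop of more than 30%, 42% or 50%. Placebo subjects will seldom do that, and the statin-intolerant stratum may hold only about 9 subjects per arm.

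A Mantel-Haenszel risk-difference interval is the estimate plus or minus 1.96 standard errors. When one arm has almost no events, the estimated standard error is unstable and the symmetric shape fits poorly. At stake is the accuracy of the headline interval for a named secondary endpoint, and whether it agrees with the test printed beside it.

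**Working it through.** **Inputs from the documents**
- SAP section 4: "assuming a difference of 19% with standard deviation of 25% between the ETC-1002 groups and the placebo group"; "38 subjects per group are required to achieve a power of 90% or higher"; "Assuming a withdrawal rate of 12.5% , the target number of subjects to be randomized was set at 44 per group".
- Protocol 6.3: "Subjects will be randomized to each group in a ratio of 1:1:1:1".
- SAP 3.3 and section 4: statin-intolerant subjects are at least 20% of the total, and 20% is assumed for sample size. 0.20 × 44 = 8.8, so about 9 intolerant and 35 tolerant per arm.

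**Inputs assumed.** The documents give neither a baseline LDL-C distribution nor an expected rate for <70 mg/dL. Mean placebo change is taken as 0. Mean active change is taken as −18.6, from the plan's own stratum effects: 0.8 × 17 + 0.2 × 25 = 18.6.

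**Step 1. The plan's own figure.** For a difference of 19 and SD 25, the noncentral t gives power 89.7% at 37 per group and 90.5% at 38. 38 / (1 − 0.125) = 43.4, rounded up to 44. The stated sample size reproduces. It concerns the primary endpoint and says nothing about responder rates.

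**Step 2. Expected placebo events.** For baseline B, the rate is Φ([(70/B − 1) × 100 − 0] / 25), times 44 for the count.

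| B (mg/dL) | Fall needed | Placebo rate | Events of 44 |
|---|---|---|---|
| 100 | 30.0% | 11.5% | 5.1 |
| 110 | 36.4% | 7.3% | 3.2 |
| 120 | 41.7% | 4.8% | 2.1 |
| 130 | 46.2% | 3.2% | 1.4 |
| 140 | 50.0% | 2.3% | 1.0 |
| 160 | 56.3% | 1.2% | 0.5 |

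Letting baseline vary between subjects (truncated normal, means 125, 135, 145) gives 1.8, 1.4 and 1.1 events. With SD 15 in place of 25, the counts fall to 0.15, 0.10 and 0.07. The whole range is therefore about 0.1 to 5.

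**Step 3. Coverage.** With n_h per arm in stratum h (35 and 9), x_h active and y_h placebo events, the weights are n_h/2, that is 17.5 and 4.5, summing to 22.
- Estimate: d = Σ (n_h/2)(x_h − y_h)/n_h / 22 = Σ(x_h − y_h)/44.
- Sato variance: (dP + Q)/22², with P = Σ(y_h − x_h)/4 and Q = Σ[x_h(n_h − y_h) + y_h(n_h − x_h)]/(4n_h).
- Interval: d ± 1.96 × √variance.

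All possible tables were enumerated exactly, with the same rates in both strata. The first three rate pairs come from assumed baseline means of 130 to 150 mg/dL (SD 20 to 30, floor 100). The last two are further sparse cases.

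| Placebo / active rate | MH coverage | Upper limit too low | Lower limit too high | Stratified Miettinen-Nurminen coverage | MH interval and CMH test disagree |
|---|---|---|---|---|---|
| 2.7% / 10.8% | 93.2% | 5.3% | 1.5% | 95.2% | 3.6% |
| 3.4% / 12.9% | 94.0% | 4.5% | 1.5% | 95.2% | 3.9% |
| 4.2% / 15.5% | 94.1% | 4.3% | 1.6% | 95.1% | 3.2% |
| 2% / 6% | 92.5% | 6.8% | 0.7% | 96.8% | 0.8% |
| 3% / 15% | 93.0% | 5.1% | 1.9% | 94.8% | 4.0% |

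The Greenland-Robins variance gives similar or slightly lower coverage (92.3% to 93.9%), so the unstated formula does not change the result. Over a grid of placebo rates 2.3% to 4.8% and active rates 10% to 20%, the MH interval covers 91.7% to 94.9% (mean 93.6%) and the stratified score interval 94.7% to 96.3% (mean 95.2%).

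**Step 4. Equal rates.** MH coverage is 99.0% at 2% in both arms, 97.1% at 3.4% and 96.0% at 4.2%. The CMH test, without continuity correction, rejects in 0.95%, 2.8% and 3.7% of trials.

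**Step 5. One data set.** Take active 6/44 (5 tolerant, 1 intolerant) and placebo 1/44 (tolerant).
- d = 5/44 = 0.114; P = −4/4 − 1/4 = −1.25; Q = 200/140 + 9/36 = 1.679.
- Variance = (−0.142 + 1.679)/484 = 0.00317, SE = 0.0563, interval 0.3% to 22.4%, which excludes 0.
- CMH: observed minus expected = 6 − 3.5 = 2.5; variance = 1.391 + 0.250 = 1.641; chi-square = 6.25/1.641 = 3.81, below 3.84.

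The interval excludes no difference, but the test is not significant at 5%. With no events in either arm, d, P and Q are all 0 and the interval has zero width.

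**The case against.** The strongest reply is that the plan is conventional: a CMH test with its matching stratified difference, foreseen in Protocol 9.4.1.3. The endpoint is secondary and outside the closed testing procedure. Clopper-Pearson intervals per arm and score intervals per stratum would show readers how sparse the data are. All of that stands and keeps the point minor.

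Several stronger readings are tempting and should be resisted.
- **That the interval under-covers in general.** It does so when the arms differ. With equal low rates it over-covers, as the score interval also does (99.0% at 2% in both arms).
- **That it inflates claims of efficacy.** In the sparse cases, lower limits are too high in 0.7% to 1.9% of trials, below the nominal 2.5%. The excess misses are upper limits set too low, which understates benefit.
- **That the CMH test is invalid.** Its size is below 5% at these rates. It is undefined when no event occurs in either arm, which happens in 17% of trials at 2% in both arms, but in only 0.2%, 0.05% and 0.01% in the first three rate pairs. An exact version would not cure conservatism.
- **That the lipid-goal endpoint has the same problem.** Its thresholds equal the entry cut-offs, so events are not rare. With an assumed baseline 10 to 30 mg/dL above threshold, placebo rates are about 18% to 40% and active rates about 43% to 68%. At 20% versus 50% and 25% versus 60%, MH coverage is 94.2% and 94.6%, and an undefined test is practically impossible.
- **That the plan expects 1 to 2 placebo events.** It gives no rate. The count depends on assumed baseline LDL-C and placebo change.

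**Conclusion.** The point holds for the overall difference in LDL-C <70 mg/dL only. If placebo events number about 1 to 2 of 44 and the drug raises the rate, the planned interval covers about 92.5% to 94% in the five cases tabulated. Its upper limit is too low in about 4% to 7% of trials. It contradicts the accompanying CMH test in about 1% to 4% of comparisons, and it collapses to zero width if neither arm has an event. These figures rest on 35 and 9 subjects per arm in the two strata, equal rates across strata, and the assumed baseline and placebo change. Only the SD of 25, the arm size and the 20% share come from the documents.

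This is a modest, cheaply removed weakness in a secondary analysis. It does not touch the primary endpoint or type I error control.

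**What to change.** In SAP 8.2, for LDL-C <70 mg/dL, compute the 95% interval for the overall difference from placebo with a stratified Miettinen-Nurminen score interval using Mantel-Haenszel weights. That matches the score approach already planned within strata and does not collapse when no events occur. Keep the CMH test, and state what is reported when neither arm has an event. A stratified Newcombe interval is a weaker choice because it overshoots, covering about 96% to 99% in these settings.

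The cost is a sentence in the SAP and a software option. The intervals will differ slightly from those now planned and will sometimes be wider.
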